Measles and Beyond: A Seroprevalence Study in Belgium, 2025-2026

Study protocol

Primary investigator: [name], Sciensano

Secondary investigators: [name], Sciensano and [name],

Sciensano

Supervisors: [name], Sciensano

[name], Sciensano

June 19th, 2025

General information

This study will be coordinated by the service Epidemiology of Infectious Diseases (contacts: [name], [name], [name] and [name]) of Sciensano. Partners of the study are volunteering laboratories from Epilabo (contact) for the collection of blood samples, UHasselt (contact: [name]) for the sample size calculation, the Immune response service (contact: [name]) and the National Reference Center (NRC) of the concerned pathogens (NRC contact) for the coordination of laboratory testing and analyses. The study is financed by the Federal Public Services for Health.

Objective of the study

The overall aim of this study is to establish a national serum bank, which will be used for a period of five years, to estimate the age-specific prevalence of biomarkers for infectious diseases in Belgium, based on priorities set by the scientific steering committee.

As a first priority, the focus will be on estimating age-specific seroprevalence of IgG antibodies against measles in Belgium, in order to inform public health interventions and possible catch-up vaccination programs.

Additional pathogens to be analyzed over the following four years will be chosen based on the prevailing public health situation. The steering committee will prioritize the potential pathogens accordingly.

Background - justification

Serological studies

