Based on seroprevalence studies, adults born in Belgium before 1970 are considered as naturally immune as the virus was omnipresent in their childhood (10,14). The MMR vaccine has been included in the childhood vaccination schedule since 1985, but coverage is thought to have been rather low initially. Therefore, to avoid outbreaks, catch-up vaccination programs are needed (15). In the Flemish Community, catch-up vaccination for all non-immune adults born after 1970 is free of charge. In contrast, in Wallonia, catch-up vaccination for adults is only partially reimbursed by the National Institute for Health and Disability Insurance (RIZIV/INAMI), which may hinder efforts to achieve universal coverage (16). While vaccination coverage for MMR1 has been ≥95% for more than 10 years, coverage for the second dose remains below the target even for the most recent birth cohorts. Current coverage stands at 82.6% nationally, with regional differences: 89% in Flanders, but only 75% in Wallonia and Brussels (17). These estimates are based on vaccination coverage surveys from 2019 and 2020, more recent information is lacking. In 2019, to increase coverage and reduce the number of susceptible children, the Belgian Superior Health Council recommended lowering the age for the second MMR dose. This was implemented in the French-speaking Community in 2020 for children aged 7-8 (instead of the previous age of 11-12) (18) and

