For each pathogen studied, we will calculate crude prevalence of seronegative, equivocal (if applicable) and seropositive results for Belgium. Since all collected samples will be tested for a certain pathogen by a single laboratory, we avoid any potential inter-laboratory variability in testing methodology. We assume that differences observed between laboratories reflect geographical variation rather than laboratory artifacts. However, since laboratories serve patients residing outside their province, the actual geographical distribution of samples may deviate from the intended stratification. To address this discrepancy, post-stratification weights will be applied to adjust for the spatial disparity between the data and the Belgian population. Moreover, seroprevalences will be adjusted for test sensitivity and specificity for the pathogen under investigation.

Statistical analysis will be done with R. Dummy tables are presented in Appendix 3. The specific analysis performed for each of the pathogens will be stored in an R file, containing explanation of the analysis. For each pathogen, these files will be stores in a secured folder at Sciensano.

Measles

For measles, measles vaccine target groups will additionally be defined as those targeted by measles vaccination (at least 1 year old and born in or after 1985) versus those not targeted (born before 1985, or not yet 1 year old at time of sampling). Within the measles vaccine-targeted group, two subgroups will be defined, with the 2-10 year olds as the ones targeted by minimal 1 dose and the 11-40 year olds as the ones targeted by 2 doses. The association between seronegativity and age group, sex, and province will be estimated using log binomial regression per measles vaccine target group. Adjusted prevalence ratios (aPR) and 95% confidence intervals (CI) will be calculated. P-values <0.05 will be considered significant.

The geometric mean titers (GMTs) for anti-measles IgG will be calculated and adjusted for clustered sampling and standardized for age, sex and population per province according to the Belgian population structure in 2025. The 95% confidence intervals (95%CI) will be estimated. Differences in GMTs between sex, region and age group will be assessed with the adjusted Wald chi-square test.

Quality assurance

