Tetanus	anti-TTIgG	 All ages, incl. 65+ 	Classic marker of vaccination coverageUnclear population immunity in elderly	
Diphtheria	Anti-DT	•	 2022-2023 outbreak in Belgium including 1 fatal case (16y) Emergence of macrolide-resistant C. Diphtheria C. Ulcerans infections in elderly 	Risk groups Belgium 2014- 2016 Belgium, 2012
CMV	anti-CMV IgG	all ageswomen reproducti ve age	 Ph3 clinical trials vaccine underway cCMV big public health impact 	Belgium 2002,2006

Appendix 2

Data collection sheet for laboratories (only seen by laboratories)

Laboratory	Nb	1
------------	----	---

Unique code	Sample date	Date of birth	Gender	Postcode
Laboratory/gender/age				
Data collection sheet delivered i	from laboratories to Scier	nsano		
Laboratory Nb 1				
Unique code	Sample A date	\ge Ge	nder Arro	ondissement
Laboratory/gender/age				

Appendix 3

Dummy tables

1. Study population characteristics

Variable	Category	N (%) – Study population	N (%) – Belgian population
Age	1-4 yo		
	5-9 yo		
	10-14 yo		
	15-19 yo		
	20-29 yo		
	30-39 yo		
	40-49 yo		
	50-59 yo		
	60-69 yo		
	≥ 70 yo		
Sex	Female		
	Male		
Provinces	Antwerp		
	West Flanders		
	East Flanders		
	Limburg		
	Flemish Brabant		
	Walloon Brabant		
	Hainaut		
	Namur		
	Liege		
	Luxembourg		
	Brussels		

2. Seroprevalence by Demographic Characteristics – one table per pathogen

Characteristic	n tested	n seropositive	% Seropositive (95% CI)
Age group (years)			
Sex			
Region/provinces			

3.	Comparison of Seroprevalence over time (with previous seroprevalence study) – one table
	per pathogen

Birth cohort	Time point	n tested	n seropositive	% Seropositive (95% CI)
Targeted by measles vaccination	Study 2013/2015			
	Study 2025/2026			
Not targeted by measles vaccination	Study 2013/2015			
	Study 2025/2026			

4. Log binomial regression analysis (Prevalence Ratios) – one per pathogen

Variable	Adjusted Prevalence Ratios (95% CI)	p-value
Age		
Sex		
Region/provinces		

Appendix 4

Scientific steering committee – Composition

Function/entity	Expertise	Number of representatives
FOD Volksgezondheid (federal authorities)	Public Health	1
DepZorg (regional authorities)	Public Health	1
AViQ (regional authorities)	Public Health	1
Vivalis (regional authorities)	Public Health	1
ONE (regional entity)	Public Health (vaccination)	1
University of Hasselt – University of Antwerpen	Biostatistics	2
University of Gent (UGent) – University Hospital of Gent (UZ Gent)	Infectious diseases (adults)	1

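### The not-targeted measles group and the 50-59 age row cross the protocol's own 1970 boundary, so the 2013-versus-2025 trend row and any 50-59 estimate mix two different adult cohorts

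*Protocol*

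**What the plan says.** The first-priority aim (Protocol, Objective of the study) is age-specific measles seroprevalence "in order to inform public health interventions and possible catch-up vaccination programs".

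The background on measles gives two adult markers before the routine-vaccination cohort begins. First, "adults born in Belgium before 1970 are considered as naturally immune as the virus was omnipresent in their childhood". Second, in the Flemish Community, "catch-up vaccination for all non-immune adults born after 1970 is free of charge". It also dates MMR in the childhood schedule from 1985.

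The analysis section (Data analysis, Measles) draws one line, at 1985. The targeted group is divided further, into ages 2-10 and 11-40. The other group is "those not targeted (born before 1985, or not yet 1 year old at time of sampling" and is not divided. Within each group, "The association between seronegativity and age group, sex, and province will be estimated using log binomial regression per measles vaccine target group".

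In Appendix 3, dummy table 3 compares 2013/2015 with 2025/2026 under a birth-cohort column with two entries. One of them is "Not targeted by measles vaccination". Dummy table 1 lists adult age rows of 40-49, 50-59, 60-69 and 70 and over. Dummy tables 2 and 4 name age as a row heading without giving bands. The sampling plan (Sample size, Table 1) treats ages 40-65 as one stratum of 1,050.

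**The concern.** People born 1970-1984 had no routine childhood MMR and are not presumed immune; people born before 1970 are presumed immune. The protocol makes that distinction itself and then puts both into one row where it compares surveys over time (objective 1.a.iv). Low seronegativity in the older cohort pulls the row down, so a gap in the 1970-1984 births looks smaller than it is.

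The mix also changes between surveys. As the oldest people pass the upper age limit, the 1970-1984 births form a larger share of the group, so the row can rise with no change in immunity in either cohort. The weighting described under Data analysis, General, adjusts for geography; standardisation for age is described only for GMTs.

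An age row of 50-59 has the same mixture, and no planned row has its boundary at 1970, where the presumption of natural immunity begins.

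**Working it through.** **Inputs.** Stratum 40-65, n = 1,050 (Sample size, Table 1; Appendix 5, Table 3). Half-width for measles in that stratum, 1.25% (Appendix 5, Table 5). Collection from mid-2025 to mid-2026, so ages are taken at about 1 January 2026. The documents give no seronegativity by birth cohort. An even spread over single years of age is assumed.

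**1. The plan's figures.** The total reproduces as the maximum per age group over three pathogens: 450 + 450 + 300 + 450 + 450 + 750 + 1,050 = 3,900. The 1.25% cannot be reproduced, because its input seroprevalence is in a figure not shown, so I invert it. From 0.0125 = 1.96 × √(q(1−q)/1,050), q(1−q) = 0.0427 and q ≈ 4.5% seronegative. This is an anchor only. The same simple formula gives 0.93 points overall (90.2% seropositive, n = 3,900) against 0.82 in Table 4, so the simulated precision is not purely binomial.

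**2. Cohort shares.** Age 40 is birth year 1985 (targeted group), ages 41-55 are 1984-1970, and ages 56 and over are before 1970.
- Stratum to age 65: 1,050/26 = 40.4 per year; 15 × 40.4 = 606 born 1970-1984, 10 × 40.4 = 404 before 1970; share w = 0.60.
- Stratum to age 64: 1,050/25 = 42 per year; 630 and 378; w = 0.625.

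**3. Dilution in a fully pooled figure.** With pre-1970 seronegativity r, the 1970-1984 value is s = (q − (1−w)r)/w, and the pooled figure shows q/s of it. The calculation ignores the 40-year-olds.

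| r (assumed) | s, w = 0.625 | q/s | s, w = 0.60 | q/s |
|---|---|---|---|---|
| 0% | 7.2% | 63% | 7.5% | 60% |
| 1% | 6.6% | 68% | 6.8% | 66% |
| 2% | 6.0% | 75% | 6.1% | 73% |
| 3% | 5.4% | 84% | 5.5% | 82% |

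The understatement is about 16-40%. The 40% end does not depend on q, since with r = 0 the ratio is simply w.

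**4. Age rows.** Ages 50-59 are births of about 1966-1975: six years from 1970 on and four before, a 60/40 mix. A 7% gap would read as 0.6 × 7 + 0.4 × 1 = 4.6% if r is 1%, or 5.0% if r is 2%. Ages 40-49 are births 1976-1985, all after 1970 (the 40-year-olds fall in the targeted group). Ages 60-69 are wholly before 1970.

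**5. Trend row.** Assume both surveys run evenly to age 65 (the 2013 range is not stated). Around the start of 2014, births 1970-1984 are ages 29-43 (15 years) and pre-1970 births are ages 44-65 (22 years), so the share is 15/37 = 41%. In 2025/2026 it is 15/25 = 60%. At constant assumed rates of 7% and 1%:
- 2013: 0.405 × 7 + 0.595 × 1 = 3.4%.
- 2025: 0.60 × 7 + 0.40 × 1 = 4.6%.

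The row moves by 1.2 points with neither cohort changing.

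**6. Precision after a split.** For 1970-1984, 1.96 × √(s(1−s)/n) with the values above gives 1.8 to 2.1 points. Power to separate the two cohorts at the 0.05 level is over 99% for r of 0-1%, 87-90% for 2%, and 41-45% for 3%.

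**The case against.** A reader might infer that all adults born before 1985 are analysed as one group and that the catch-up aim is answered with a diluted figure. The documents do not support that. The target groups are an addition to the general analysis. Age group is a covariate in the regression within each target group. The aim is stated as age-specific, and seroprevalence and GMTs are to be reported or compared by age group. A gap in people in their forties would show undiluted in a 40-49 row, and a 60-69 row bears on the presumption of immunity before 1970.

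Nor is the 1985 line a contradiction: it follows the start of the childhood programme. Catch-up eligibility in the background also covers non-immune adults born from 1985 on, so it is not a property of the 1970-1984 births alone.

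The adult bands in dummy table 1 describe the study population. The bands for the results are not given and may be set in an analysis plan not at hand, so the point on 50-59 holds only if that row is carried into the results. The cohort-specific rates are assumptions throughout.

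All of this stands and narrows the point. It does not remove the mixture in dummy table 3, where the protocol itself fixes the rows by birth cohort and leaves out the boundary that its background uses.

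**Conclusion.** The point holds for the not-targeted row of dummy table 3 and for any 50-59 estimate; it does not extend to the age-specific analysis as a whole. A fully pooled figure would understate the 1970-1984 seronegative share by about 16-40%. That rests on 4.5% pooled seronegativity (inferred from Table 5), an even age spread, and pre-1970 seronegativity of 0-3%. The trend row carries a further risk from changing composition, illustrated by 3.4% to 4.6%; the actual shift depends on the age mix of the 2013 survey. This is a worthwhile, inexpensive improvement rather than a flaw that undermines the study.

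**What to change.** In Data analysis, Measles, and in dummy table 3, split the not-targeted adults into born before 1970 and born 1970-1984, and report both surveys by these rows. State which side birth year 1970 falls on, since the background speaks only of before and after. In the seroprevalence, GMT and prevalence-ratio outputs, place an adult age boundary at about 55/56 years. Spread the 1,050 samples aged 40-65 over both cohorts. Do not label only the 1970-1984 row as eligible for catch-up, because the background extends that to all non-immune adults born after 1970.

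Birth year can be approximated from age in years and the sample date on the sheet sent to the sponsor (Appendix 2). Figure 1 of Appendix 5 already presents the 2013 data by birth year.

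The cost is a change of definition, an extra row in dummy table 3, and wider intervals than for the pooled group (about ±1.8 to 2.1 points for 1970-1984). Because date of birth is not transferred, people near the cut can be misplaced by about one birth year, and a fixed age boundary drifts by a similar amount over the collection year. No extra samples are needed.

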For measles, the most recent national serological survey was conducted in 2013. To evaluate the sample size needed to estimate the current seroprevalence by age, we use a cohort-based modelling approach to project immunity levels to 2025. This model incorporates historical vaccination coverage, age of vaccination and waning immunity, following methods described by Hens et al. (2015) and Abrams et al. (2014) (30,31). The aim was to obtain both overall and agegroup-specific seroprevalence estimates with a precision of +-2% (width of confidence interval max. 4%). To ensure sufficient sample size of the serumbank for pathogens other than measles, these calculations were repeated for 2 additional pathogens. The additional pathogens (CMV and Hepatitis B) were selected based on their seroprevalence patterns in the population who differ importantly from the measles seroprevalence patterns.

Appendix 5 contains the full methodology and results. With a total sample size of 3,900 samples, precision of overall national seroprevalence estimates for all 3 pathogens would be <2% (and even <1% for measles and Hepatitis B). Not all agegroup-specific estimates would have <2% precision, but all are within acceptable ranges (all <3% precision for measles). To obtain equal precision in the region-specific estimates, similar absolute number of samples would need to be collected from Flanders, Walllonia and Brussels. However, as both the population size as well as

the number of labs in Brussels is much smaller than in Flanders, this is deemed unfeasible. We therefore plan a pragmatic approach and adjust the regional allocation to reflect practical constraints and the actual number of participating laboratories, accepting wider confidence intervals in Brussels. The final distribution of samples by agegroup is then presented in Table 1.

Table 1. Samples distribution - National

Age groups	Number of samples - National
1-4yo	450
5-9yo	450
10–14yo	300
15-19yo	450
19-31yo	450
31-40yo	750
40-65yo	1050
Total	3900

Sample collection and analysis

Sample collection and transport

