University of Brussels (ULB) - University Hospital of St Pierre	Infectious diseases (adults)	1
Catholic University of Louvain-la- Neuve (UCL) – University Hospital of Dinant Godinne UCL Namur	Infectious diseases (children)	1
University Hospital of Brussel (UZ Brussel)	Infectious diseases (children)	1
University of Brussels (ULB) – Plotkin institute	Immunology	1
Sciensano	Public Health	3
	Biostatistics	
	Microbiology	
Representatives of the Epilabo network	Clinical microbiology	7

Scientific steering committee - Role

Provide input and feedback on main aspects as study, such as

- Choice of pathogens and priority research questions
- Methodology aspects
- Any technical issues that might arise
- Interpretation of results and preparation of communication and publication
- If applicable, evaluate external demands on the use of the serumbank

To be able to fulfill this role, it is expected that the selected committee members will participate to ca. 1 meeting / year in addition to provide ad-hoc written input (through e-mail) if required.

Appendix 5

Allocation of serological samples

The distribution of age-stratified samples follows the simulation-based framework developed by Blaizot et al. (2019) [1]. More specifically, the procedure aims to optimize the precision with respect to seroprevalence estimators (based on single cross-sectional serological survey data) for a fixed total sample size (i.e., number of blood serum samples collected in a random fashion). Using statistical and mathematical models, we compare several age-based sampling structures: (i) a survey-based age distribution corresponding to the observed age patterns in previous serological surveys, (ii) a population-based structure proportional to the current demographic age distribution, and (iii) a uniform age structure with equal sampling probabilities across different age groups. These strategies will be evaluated to determine which approach provides the most accurate and precise seroprevalence estimates. In addition, we compute the optimal number of samples to allocate within each age group in order to minimise uncertainty in the final estimates. We apply this method to three pathogens—measles virus, hepatitis B virus and cytomegalovirus—selected for their distinct sero-epidemiological profiles and the availability of historical serological data. These pathogens provide representative models for the wider range of infections covered by the multiplex test.

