To ensure sufficient precision for all pathogens, we selected the maximum number of samples per age group across the three pathogens as the final recommendation. This results in a total of 3,900 samples nationally, which we divide equally across the three regions, yielding 1,300 samples per region.

Table 4 reports the expected precision of the overall seroprevalence estimates under this allocation. At the national level (3,900 samples per pathogen), the expected precision is 0.82% for measles, 0.85% for hepatitis B, and 1.69% for CMV. At the regional level (1,300 samples per region), expected precision decreases slightly to 1.69% for measles, 1.45% for hepatitis B, and 2.64% for CMV, still within acceptable bounds.

Age group	Measles	НерВ	CMV
1-4yo	5%	5%	15%
5-9yo	15%	15%	5%
10-14yo	5%	10%	10%
15-19yo	15%	5%	10%
19-31yo	15%	10%	10%
31-40yo	20%	25%	15%
40-65yo	25%	30%	35%
Precision	0,88%	0,74%	1,52%

Table 2. Optimal proportion of samples per age group for measles, hepatitis B, and CMV based on national-level simulations.

	Measles	НерВ	CMV	National	Regional
1-4yo	150	150	450	450	150
5-9yo	450	450	150	450	150
10-14yo	150	300	300	300	100
15-19yo	450	150	300	450	150
19-31yo	450	300	300	450	150
31-40yo	600	750	450	750	250
40-65yo	750	900	1050	1050	350
Total	3000	3000	3000	3900	1300

Table 3. Absolute number of samples per age group, assuming 3,000 samples per pathogen. The final allocation (bold values) corresponds to the highest required count across pathogens, resulting in a total of 3,900 samples nationally (or approximately 1,300 per region).

	Measles	НерВ	CMV
National	0,82%	0,85%	1,69%
Regional	1,69%	1,45%	2,64%

Table 4. Expected precision (half-width of the 95% simulation-based confidence interval) for overall seroprevalence estimates under the final allocation. National precision is based on 3,900 samples; regional precision is based on 1,300 samples per region.

Precision by age - national allocation

_	.=			
Age group	Allocation	Measles	НерВ	CMV
1-4yo	450	2,25%	0,50%	4,23%
5-9yo	450	2,61%	0,53%	3,25%
10-14yo	300	1,76%	0,63%	3,50%
15-19yo	450	1,95%	0,73%	3,14%
19-31yo	450	2,88%	1,20%	2,94%
31-40yo	750	2,40%	1,51%	2,78%
40-65vo	1050	1,25%	1.42%	3.02%

Table 5. Expected precision (half-width of the 95% simulation-based confidence interval) for prevalence estimates of each age group under the final allocation.

4. References of Appendix 5

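### The protocol adjusts only the geometric mean titres for clustering by laboratory; prevalence ratios, seroprevalence intervals and the stated precision make no such allowance

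*Protocol*

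**What the plan says.** **Design.** Under Sampling method and Sampling procedure, leftover sera are a convenience sample. All 52 laboratories of the sentinel network are invited, and each participant receives a fixed quota by age and sex. How many will take part is not known.

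**Analysis.** Under Data analysis – Measles, the GMTs "will be calculated and adjusted for clustered sampling and standardized for age, sex and population per province". For the prevalence ratios the text is: "The association between seronegativity and age group, sex, and province will be estimated using log binomial regression per measles vaccine target group", with 95% confidence intervals and a 0.05 significance level. Under Data analysis – General, the seroprevalences receive post-stratification weights and a correction for sensitivity and specificity. Neither passage mentions clustering. The General part adds: "We assume that differences observed between laboratories reflect geographical variation rather than laboratory artifacts".

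**Precision.** The Sample size section states "precision of overall national seroprevalence estimates for all 3 pathogens would be <2% (and even <1% for measles and Hepatitis B". Appendix 5 gives the figures: "At the national level (3,900 samples per pathogen), the expected precision is 0.82% for measles, 0.85% for hepatitis B, and 1.69% for CMV". Appendix 5 describes the sample size as the "number of blood serum samples collected in a random fashion". Its section 1.4 draws each person's serostatus from a Bernoulli distribution that depends on age only.

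**The concern.** Samples from one laboratory share a catchment area, a mix of patient sources (emergency, surgical, ENT, general practice) and pre-freezing handling. If seropositivity varies between laboratories beyond age, sex and province, 3,900 such samples carry less information than 3,900 independent ones. By adjusting the GMTs, the protocol accepts this for one outcome. The seroprevalences and prevalence ratios use the same sera.

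Two things are at stake. First, the stated precision, which supports the choice of 3,900 samples, may be too favourable. Second, intervals and p-values for province may be too optimistic. Province results matter because the study aims to identify geographical immunity gaps and to direct vaccination campaigns.

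**Working it through.** **1. Reproduce the stated measles precision.** Appendix 5, Table 5 ("Expected precision (half-width of the 95% simulation-based confidence interval) for prevalence estimates of each age group under the final allocation") gives measles half-widths d of 2.25, 2.61, 1.76, 1.95, 2.88, 2.40 and 1.25% for n = 450, 450, 300, 450, 450, 750 and 1,050. Combining the age groups as independent strata with weights W = n/3,900:

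√Σ(W²d²) = √(0.0674 + 0.0907 + 0.0183 + 0.0506 + 0.1104 + 0.2130 + 0.1133) = 0.815%, against 0.82% stated.

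This agrees with the simulation as described, which has no laboratory term. The same formula does not reproduce hepatitis B (0.52% against 0.85%) or CMV (1.28% against 1.69%). Simple random sampling, 1.96√(p(1−p)/3,900), gives 0.72% at p = 0.055 and 1.50% at p = 0.348. For those two pathogens the absence of a design effect rests on the described method, not on a numerical match.

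**2. Design effect on the national figures.** DEFF = 1 + (m−1)×ICC, and the half-width is multiplied by √DEFF. With 52 laboratories m = 3,900/52 = 75; with 26 (an assumption: half of them) m = 150. The ICC is also an assumption. Equal quotas are a simplification; unequal ones would raise DEFF.

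| Laboratories | ICC | DEFF | Measles | Hepatitis B | CMV |
|---|---|---|---|---|---|
| 52 | 0.001 | 1.07 | 0.85% | 0.88% | 1.75% |
| 52 | 0.005 | 1.37 | 0.96% | 0.99% | 1.98% |
| 52 | 0.01 | 1.74 | 1.08% | 1.12% | 2.23% |
| 52 | 0.02 | 2.48 | 1.29% | 1.34% | 2.66% |
| 26 | 0.001 | 1.15 | 0.88% | 0.91% | 1.81% |
| 26 | 0.005 | 1.75 | 1.08% | 1.12% | 2.23% |
| 26 | 0.01 | 2.49 | 1.29% | 1.34% | 2.67% |
| 26 | 0.02 | 3.98 | 1.64% | 1.70% | 3.37% |

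**3. ICC at which each claim fails.** Solve ((limit/stated)² − 1)/(m−1).

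- Measles, limit 1%: ((1/0.82)² − 1)/74 = 0.0066; with 26 laboratories (divide by 149), 0.0033.
- Hepatitis B, limit 1%: 0.0052 and 0.0026.
- CMV, limit 2%: 0.0054 and 0.0027.

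**4. Age groups.** Few samples per age group come from one laboratory, so the effect is smaller. For ages 19–31, m = 450/52 = 8.65. At ICC 0.02, DEFF = 1.153 and 2.88% becomes 3.09%, just above the stated bound of 3% for measles.

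**5. Error rate of a nominal 5% test.** The regressions are run separately by vaccine target group, so the cluster size is the number per laboratory within that group. In Table 1 the 40–65 group (1,050) roughly matches the non-targeted group, and the other 3,900 − 1,050 = 2,850 the targeted group. For a covariate constant within each laboratory, the error is 2×(1 − Φ(1.96/√DEFF)). With 52 laboratories:

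- Targeted, m = 54.8: DEFF 1.27 to 2.08 for ICC 0.005 to 0.02; error 8% to 17%.
- Non-targeted, m = 20.2: DEFF 1.10 to 1.38; error 6% to 10%.

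At ICC 0.001 the same formula gives 5.6% and 5.2%. Under equal quotas these are upper bounds for province, because patients of one laboratory can live in different provinces.

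**The case against.** **The variance method may simply be unstated.** The protocol names a regression family and promises an annotated R file per pathogen; an analysis plan that is not shown may specify robust variance. This stands in part. A reader might infer that the intervals will be computed as if the samples were independent, but the protocol does not say so. What it does show is a cluster adjustment written for one outcome and omitted for the others. The precision figures are different: they are stated results of an independent-draw simulation, and a later plan cannot alter how they were obtained.

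**The size is assumed.** This stands. Neither the ICC nor the number of participating laboratories is in the document, and at ICC 0.001 the claim of under 1% survives for measles and hepatitis B with 52 or 26 laboratories.

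**Error rates could be overstated.** Using all 75 samples per laboratory would give 9% to 21% at ICC 0.005 to 0.02, but the regressions are run per target group, so those rates do not apply. Nor do inflated rates extend to every coefficient: age and sex are quota-balanced within laboratories, so a shared laboratory effect largely cancels. Province is taken from the patient's postcode, and the protocol notes that laboratories serve patients from other provinces. It is therefore largely, but not wholly, a between-laboratory factor.

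**The sentence on laboratory artefacts follows the one on single-laboratory testing**, so it most naturally concerns assay variability. That is fair, but as worded it also covers differences in patient mix, which central testing does not remove.

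**Robust variance does not remove case-mix bias.** Correct. Fifty-two laboratories over the 11 areas in Appendix 3 is 52/11 = 4.7 each, so robust inference for province also needs a small-sample correction.

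**Conclusion.** The point holds as an inconsistency in the analysis text and as an unstated assumption behind the precision figures. The documents support three conclusions. The cluster adjustment is given for GMTs only. The precision in the Sample size section and in Table 4 assumes independent sampling. Province ratios are the results most exposed.

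The size is conditional. The thresholds in step 3 are low, so the claims of under 1% (measles, hepatitis B) and under 2% (CMV) are not secure, but they are not shown to be false. Overall measles precision stays within the ±2% aim across the assumed ICC range with 52 or 26 laboratories, so the sample size for the priority pathogen is not undermined nationally. A reader might infer that province findings will mostly be laboratory artefacts; the documents give no between-laboratory variance from which to conclude that.

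**What to change.** 1. In Data analysis, extend the cluster adjustment stated for GMTs to all seroprevalence intervals and prevalence ratios: laboratory as primary sampling unit, robust variance with a small-sample correction, and degrees of freedom based on the number of laboratories. Add a model with a laboratory random intercept as a sensitivity analysis.
2. Limit the sentence on geographical variation to assay variability, and state that differences between provinces may also reflect laboratory case-mix. The variance correction does not cure that bias, so it belongs in the interpretation.
3. In the Sample size section and Appendix 5, Table 4, label the precision as assuming independence. Add a range over the ICC and the number of laboratories that join; Table 5 and the under-3% statement for measles age groups need the same label.

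Sampling and testing do not change. The laboratory number is already part of the sample code, so the work is wording plus one survey-design specification in R. The price is wider intervals and less favourable stated precision.
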